3.2. Group 2: Non-pregnant, non-lactating females of child bearing potential

Objectives	Endpoints
Primary	

 To evaluate the safety and tolerability of IH and IV oxytocin. 	
 General safety parameters: adverse events; absolute values and changes over time of vital signs (blood pressure, heart rate) and 12-lead electrocardiogram (ECG) parameters (PR, QRS, QT, Corrected QT interval [QTc] intervals) from pre-dose values. Specific respiratory safety parameters: adverse respiratory events as monitored by spirometry including Forced expiratory volume at 1 minute (FEV1.0), respiratory rate, and pulse oximetry.

 To characterize the pharmacokinetics of single doses of IH oxytocin and 5 I.U. IV oxytocin. 	
 Plasma concentration time profile for IH oxytocin and 5 I.U. IV oxytocin. PK parameters: C_{max}, C_{p10}, C_{p20}, C_{p30}, t_{max}, AUC, Plasma clearance (CL), volume of distribution and t_{1/2} will be calculated as data permit.
Exploratory	

 To evaluate endogenous plasma oxytocin concentrations in non-pregnant females in the presence and absence of the combined oral contraceptive. 	
 Pre-dose plasma concentrations of oxytocin.

 To compare the IH pharmacokinetics of oxytocin between Cohort A (subjects on combined oral contraceptive) and Cohort B (subjects using a non-hormonal form of contraception). 	
 C_{p10}, C_{p20}, C_{p30}, C_{max}, AUC(0-3h), Area under the concentration-time curve from time zero to infinity (AUC[0-∞]) and t_{1/2}, will be compared as data permit.

 To compare the IV pharmacokinetics of oxytocin between Cohort A and Cohort B. 	
 C_{max}, AUC, t_{1/2}, CL and Volume of distribution (VOD) will be compared as data permit.

[figure not shown]
3.3. Groups 1 and 2: Women in TSL and Non-pregnant, non-lactating females of child bearing potential

Objectives	Endpoints
Exploratory	

 To compare pharmacokinetics of IH oxytocin between Group 1 and Group 2. 	
 Cp10, Cp20, Cp30, Cmax, AUC(0-3h) AUC(0-∞), and t1/2 will be compared as data permit.

[figure not shown]

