	
the literature but IV administered oxytocin can have a vasodilatory and negative inotropic effect in humans. Hypotension is thought to arise as a result of vascular smooth muscle relaxation and oxytocin binding to cardiac atrial OTR which leads to atrial natriuretic peptide (ANP) being transiently released into the systemic circulation.
 
Prolongation of the QTc interval has been reported at the time of caesarean delivery with 10 IU IV oxytocin administration, rather than IM injection, in susceptible individuals
	
as study treatment. Telemetry and frequent 12-lead ECGs will be used to monitor the healthy subject cohorts
 
The 5 IU IV dose of oxytocin is the standard dose administered at the Rosie Maternity hospital post Caesarean Section.
 
IV bolus will be given as a slow IV injection over 30 seconds with the option to change to a 5 minute infusion if frequent CV adverse effects are observed
 
Exclusion of subjects with long QT syndrome, congenital cardiac abnormalities, and subjects taking anti-arrhythmic drugs.
 
12-lead ECG and telemetry covering Cmax in healthy subjects administered IH, IM and IV oxytocin

Insufficient uterotonic effect	The altered physiology and pharmacokinetics of women in the TSL may lead to a sub-optimal dose of inhaled oxytocin, resulting in a reduced or absent uterotonic effect.	
In this setting, women in TSL and post-delivery are intensively observed. Therefore, any adverse events, including excessive blood loss due to unenhanced uterine contraction, will be managed in accordance with current local practice guidelines. This will usually include administration of additional uterotonic agents in the first instance.
 
A follow-up within 24 h of discharge by the study team will be performed to specifically enquire if any late bleeding problems had occurred.

Potential Risk of Clinical Significance	Summary of Data/Rationale for Risk	Mitigation Strategy
		An interim analysis of IH and IM PK in the TSL group will be performed to ensure that the PK is in the acceptable range for efficacy to be anticipated.
Reference Intervention - IM Oxytocin / IV Oxytocin		
Hypotension, tachycardia and prolongation of QTc interval	See above section.	See above section. Subjects receiving the IV Oxytocin are required to have a systolic BP \geq 90 Millimeter of mercury (mmHg) prior to dosing.

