Myocardial Ischaemia and ST change on ECG	ECG changes consistent with myocardial ischaemia have been observed with 10 IU oxytocin IV bolus in healthy women associated with hypotension and tachycardia.	Oxytocic cardiovascular effects appear to be transient and persistent myocardial damage very rare and associated with 10 IU IV. Study is only using 5 IU IV as a slow IV bolus which is associated with a short lived increase in heart rate and reduction in BP but not ST changes on ECG in women undergoing Caesarean Section. Telemetry and 12-lead ECG monitoring in healthy subjects.
Abdominal pain	There is a hypothetical risk that IM oxytocin may trigger abdominal pain through contractions of the non-pregnant uterus in healthy women. Given the short half-life of oxytocin (approximately 30 minutes), the duration of a single abdominal pain episode would be expected to be brief, not sustained and not	This is a theoretical possibility and not expected to occur. Ongoing assessments of study subjects' well-being along with vital signs and laboratory evaluations will be completed throughout the duration of the study. Abdominal pain which is clinically uncomfortable to the subject may be treated with paracetamol at the local investigator's discretion.

Potential Risk of Clinical Significance	Summary of Data/Rationale for Risk	Mitigation Strategy
	recurrent in the absence of further oxytocin administration. Furthermore, no abdominal pain was observed in the FTiH study.	

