6.4. Planned Dose Adjustments

There is no plan to adjust the dose of IH oxytocin in this study. However, if systemic exposure seen in 400 mcg IH oxytocin in TSL subjects is less than expected and not comparable to the 10 I.U. IM profile, a consideration to escalate the dose to 600 mcg may be made as detailed in Section 6.4.1.

For Group 2, if an exaggerated physiological response is seen with the IV dose, such as increased heart rate and decreased blood pressure, then consideration will be given to changing to a 5-minute infusion.

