7.1.2. Time and Events – Main Phase Procedures**Group 1**

Procedure	Pre-dose	Time post dose										
		3 min	5 min	10 min	15 min	20 min	30 min	1 hr	2 hr	2.5 hr	3 hr	4 hr
Vital signs ¹							X		X			
Pharmacokinetic blood sample	X ²	X	X	X	X	X	X	X	X	X	X	X
Prior medication review	X											
Concomitant medication review		----- continuous review -----										
AE review		----- continuous review -----										
SAE Review		----- continuous review -----										
Device Acceptability Questionnaire ³												X
Full Blood Count	X											X

1. Includes blood pressure, heart rate, temperature, respiratory rate
2. Predose PK sample to be taken immediately prior to administration of study treatment
3. Only to be administered when randomized to IH oxytocin

Group 2 – Sessions 1 and 2

Procedure	Pre-dose	Time Post Dose														
		2 min	3 min	5 min	8 min	10 min	15 min	20 min	30 min	45 min	1 hr	1.5 hr	2 hr	2.5 hr	3 hr	4 hr
Brief Physical Exam	X															
Pregnancy Test	X															
Alcohol Breath Test, Smokerlyzer, Urine Drug Screen ¹	X															
Vital signs ²	X			X			X		X		X					X
12-lead ECG	X	X					X		X	X		X				X
Cardiac Telemetry		-----Continuous-----														
Spirometry ³	X											X				
Pharmacokinetic blood sample	X ⁵	X	X	X	X	X	X	X	X	X	X	X	X	X	X	X
Immunogenicity Sample	X															
Laboratory assessments (including liver chemistries)	X															X
Prior medication review	X															
Concomitant medication review		-----continuous review-----														
AE review		-----continuous review-----														
SAE Review		-----continuous review-----														
Discharge from unit ⁴																X

1. Smokerlyzer at Principal Investigator (PI)/designee discretion if smoking history in question.
2. Includes blood pressure, heart rate, temperature, respiratory rate, and SpO₂
3. FEV 1.0 will be performed in triplicate at each time point. Record all three values on source document, and record best effort in eCRF.
4. Discharge at PI discretion, no sooner than 4-hours post-dose.
5. 3 pre-dose samples: approximately 1 hr pre-dose, 30 minutes pre-dose, and 15 minutes pre-dose

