7.3.9. Continuous Cardiac Telemetry (Group 2 Only)

Continuous cardiac telemetry will be started at least 10 minutes pre-dose (to obtain a stable reading) and continue until at least the first hour after IV and IH placebo / oxytocin administration and then as deemed necessary by the investigator. Full disclosures will be reviewed in detail and the review maintained as part of the subject's source documents.

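### Group 2 schedules no blood pressure in the first 5 minutes after dosing, so the peak fall after the 30-second IV bolus can be missed or understated

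*Protocol*

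**What the plan says.** The primary safety endpoint for Group 2 (section 3.2) includes "absolute values and changes over time of vital signs (blood pressure, heart rate) and 12-lead electrocardiogram (ECG) parameters", for both the inhaled (IH) and IV routes.

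Section 4.6.1 describes the IV dosing: "IV bolus will be given as a slow IV injection over 30 seconds with the option to change to a 5 minute infusion". Its myocardial ischaemia row says the study uses "5 IU IV as a slow IV bolus which is associated with a short lived increase in heart rate and reduction in BP". Section 4.5 says adverse events correlate with Cmax and names a transient drop in blood pressure among the effects. It also says the 5 I.U. IV dose is included so that the inhaled product's safety and PK can be assessed against the IV route.

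As mitigation, section 4.6.1 lists ongoing blood pressure, heart rate and ECG assessment, and then "12-lead ECG and telemetry covering Cmax in healthy subjects administered IH, IM and IV oxytocin". Blood pressure is not named in that last statement.

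In the Group 2 table of section 7.1.2, vital signs fall pre-dose and at 5, 15 and 30 minutes, 1 hour and 4 hours. The footnote to that row begins "Includes blood pressure, heart rate, temperature, respiratory rate". The 12-lead ECG and the PK samples both have a 2 minute time point, and PK has a further one at 3 minutes. Section 7.3.9 runs telemetry from at least 10 minutes before dosing to at least 1 hour after.

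Section 6.4 says a change in how the IV dose is given will be considered "if an exaggerated physiological response is seen with the IV dose, such as increased heart rate and decreased blood pressure".

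**The concern.** The protocol's own reasoning points to the minutes around the IV peak: harm follows Cmax, and the fall in pressure does not last. It acts on that reasoning for ECG, telemetry and PK, but not for blood pressure. Hypotension is a listed risk, and it is the one cardiovascular sign in the primary endpoint with nothing scheduled to measure it in that interval.

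Three things depend on the reading. The first is the blood pressure part of the primary endpoint after IV. The second is the IV arm as the safety comparator for the inhaled product: if the early IV fall is under-recorded and the inhaled fall is not, the comparison is affected unequally. The third is one of the two example signs that section 6.4 gives for reconsidering IV administration.

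**Working it through.** No sample-size or interval calculation is involved. The check is of timing, followed by a labelled illustration.

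**Timing, from the documents**

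- End of IV bolus: 0.5 min (sections 4.6.1 and 6.1, Table 1).
- First ECG and first PK sample: 2 min, which is 2 − 0.5 = 1.5 min after the bolus ends.
- First blood pressure: 5 min, which is 5 − 0.5 = 4.5 min after the bolus ends.
- Inhaled tmax in the first-in-human study: 0.05 to 0.50 h (section 4.5), which is 3 to 30 min. Readings at 5, 15 and 30 min cover most of that range.

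**How many readings catch an effect of a given duration**

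With blood pressure at 5, 15, 30, 60 and 240 min, a fall that ends before 5 min is caught by no reading. One that lasts 5 to under 15 min is caught by one. One that lasts 15 to under 30 min is caught by two. The protocol calls the IV effect brief but gives no minutes, so it does not say which case applies.

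**What the stated half-life implies**

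The abdominal pain row of section 4.6.1 gives a half-life of about 30 min. The fraction of concentration left 4.5 min after the bolus ends is 2^(−4.5/30) = 0.90. If the early decline were faster, with assumed half-lives of 10, 5, 3, 2 or 1 min, it would be 0.73, 0.54, 0.35, 0.21 or 0.04. These are concentrations, not blood pressures. The protocol defines t1/2 as a terminal-phase quantity, so 0.90 need not describe the first minutes after a bolus.

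**Illustration only**

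Assume a nadir at 1 min and exponential recovery with half-time h. Neither assumption is in the protocol. The share of the peak fall still visible at time t is 0.5^((t − 1)/h).

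| h (min) | at 5 min | at 2 min |
|---|---|---|
| 1 | 6% | 50% |
| 2 | 25% | 71% |
| 3 | 40% | 79% |
| 5 | 57% | 87% |
| 10 | 76% | 93% |
| 30 | 91% | 98% |

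The 5 minute reading could show almost none or nearly all of the fall, depending on a quantity the protocol does not give. If the nadir came at about 5 min, the existing reading would catch it in full. The table shows that the schedule leaves the answer open; it does not estimate the loss.

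**The case against.** A reader might infer that the 5 minute reading comes after the fall is over, so that the endpoint misses the effect it monitors. The documents do not support that. They give no onset, nadir or duration, and the only half-life stated would leave about 90% of the concentration at that point. Correlation with Cmax concerns the size of exposure; it does not say when pressure is lowest. Section 4.6.1 attributes hypotension partly to smooth-muscle relaxation and natriuretic peptide release, which need not coincide with the plasma peak. This objection stands and limits the claim to what can be missed or understated.

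Nor is a promise broken. The statement about covering Cmax names ECG and telemetry only, and the schedule provides both. That also stands: the mismatch is between the protocol's rationale and its blood pressure schedule, not between two explicit commitments.

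It can also be said that the section 6.4 signs will not go unnoticed, since heart rate is monitored continuously, adverse events are reviewed continuously, and blood pressure is one example among possible signs. This is largely right. A purely early fall in pressure without other signs is what could escape.

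Finally, sections 7 and 7.3 allow time points to be changed or added, and section 7 does so by a note to file. That makes the remedy easy but does not close the gap. Both provisions rest on new data becoming available, and a fall that is not measured supplies none.

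**Conclusion.** The point holds as a cheap improvement to the design, not as an error that invalidates the endpoint. In Group 2 no blood pressure is scheduled until about 4.5 minutes after the IV bolus ends, although the protocol treats the period around Cmax as the one that matters for safety and describes the fall as brief. The schedule can therefore miss or understate the peak fall after IV. It does so less after inhalation, and heart rate is covered by the 2 minute ECG and telemetry.

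The size is unknown. It depends on the time of the nadir and the speed of recovery, neither of which is documented, so the percentages above are illustrative and no figure in mmHg can be supported. A firm claim that the comparison between routes is distorted would likewise go too far. Safety is summarised descriptively (section 9.4.1.1), and what can be said is that any under-recording would fall mainly on the IV side.

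**What to change.** In the Group 2 table of section 7.1.2, add a blood pressure and heart rate reading at about 2 minutes post-dose in both sessions, beside the existing 2 minute ECG and PK sample. Include it in the summaries of change from pre-dose. If the sponsor prefers to keep the present schedule, the protocol should say why a first reading at 5 minutes is adequate for a 30-second bolus.

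The cost is one cuff reading per session: 2 × 10 = 20 readings for the planned 10 women, with no additional invasive procedure. The drawback is crowding. Section 7 recommends ECG, then vital signs, then the blood draw at its exact nominal time, and another draw follows at 3 minutes. Allowing the reading to be taken at about 2 minutes, and placing the cuff so that it does not interfere with the sampling cannula, deals with most of this. Section 7.3.6 asks for 5 minutes of semi-supine rest before vital signs, so rest would have to begin at least 5 − 2 = 3 minutes before dosing.

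No change to any dose or to the section 6.4 rule is proposed.

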4.6.2. Immunogenicity Risk

The oxytocin material used in the inhaled product is produced synthetically and so does not include any other protein/cell impurities which might be intrinsically immunogenic. A review of the risk of immunogenicity of oxytocin and/or excipients was considered as part of the non-clinical safety studies but as the lymphoid tissues were not deemed to be pathologically affected and there were difficulties in generating a suitable assay, anti-drug antibodies (ADAs) were not measured. The FTiH study involved repeat dosing, and did not reveal any unexpected differences in PK which may have signalled the development of ADAs.

Oxytocin is an endogenous human peptide with a short systemic half-life and there are no reports of immunogenicity with oxytocin via parenteral administration. Thus it is considered unlikely that inhaled delivery of a small molecular weight (MW) peptide molecule like oxytocin would invoke an immunogenic response.

However, blood samples will be retained for anti-oxytocin antibody analysis if required in the event of an anaphylactic / allergic reaction (refer to Section 5.4.2) or other observation which would suggest an immunogenic effect.

4.6.3. Benefit Assessment and Overall Benefit:Risk Conclusion

Oxytocin has been administered to postpartum women for over 40 years via both the IM and IV routes, and has an established safety profile for each of these routes of administration. The FTiH study into IH oxytocin revealed no safety concerns for any of the subjects who received this new formulation. There are no direct clinical benefits to the volunteers within this study. The main contribution to their participation will be in the further development of a therapy (i.e. inhaled oxytocin) which may be ultimately used as a preventative therapy for postpartum haemorrhage in women during TSL in resource poor settings. It is fundamental to the project to clearly understand the PK of oxytocin following IH and IM administration to women in TSL in order to confirm the dose level that delivers a PK profile comparable to that of 10 I.U. IM (i.e. current standard of care in the developed world setting). Taking into account the measures taken to minimize risk to subjects participating in this study, the potential risks identified in association with oxytocin (IH IM, and IV) are justified by the supporting data and overall benefit anticipated for women's health worldwide.

5. SELECTION OF STUDY POPULATION AND WITHDRAWAL CRITERIA

Specific information regarding warnings, precautions, contraindications, adverse events, and other pertinent information on the GSK investigational product or other study treatment that may impact subject eligibility is provided in the investigator brochure for GR121619 [GlaxoSmithKline Document Number [2015N240749_01](#)] and SPC for oxytocin administered IM or IV.

Deviations from inclusion and exclusion criteria are not allowed because they can potentially jeopardize the scientific integrity of the study, regulatory acceptability or subject safety. Therefore, adherence to the criteria as specified in the protocol is essential.

5.1. Inclusion Criteria

A subject will be eligible for inclusion in this study only if all of the following criteria apply:

AGE

All Groups:
 
 Between 18 and 40 years of age inclusive, at the time of signing the informed consent.

TYPE OF SUBJECT AND DIAGNOSIS INCLUDING DISEASE SEVERITY

All Groups:
 
 Healthy as determined by the investigator or medically qualified designee based on a medical evaluation including medical history, physical examination, and laboratory tests as required per protocol. Note: At time of randomisation, investigator or designee should confirm the subject feels fit and well, and is safely able to participate in the study. Subject clinical chemistry and haematology values within an acceptable range for the population recruited and not of abnormal clinical significance. Note: Additional laboratory tests beyond those which are done as part of routine care (e.g. 28-week visit) are not required for subjects in Group 1. The investigator/designee may use his/her judgment in deciding whether to perform additional laboratory assessments to determine eligibility. 
A subject with a clinical abnormality or laboratory parameter(s) which is/are not specifically listed in the inclusion or exclusion criteria, outside the reference range for the population being studied may be included only if the investigator in consultation with the Medical Monitor (if required) agree and document that the finding is unlikely to introduce additional risk factors and will not interfere with the study procedures.
 
 Adequate peripheral venous access for cannulation.

Group 1 Only:

5. Currently pregnant, with an uncomplicated pregnancy as determined by the investigator or designee.
6. Estimated date of delivery within 24 weeks of screening.
7. Planned spontaneous vaginal birth and considered by investigator at low risk for PPH.
8. Planned birth in between the 37th and 42nd week of pregnancy.

Note: Subjects can only receive study treatment if the onset of labour is between approximately 37 and 42 weeks estimated gestation. If a subject goes into labour before or after this timeframe, she should not receive study treatment.

9. Women who qualify for oxytocin as appropriate for active management of TSL and who agree to have active management.

Group 2 Only:

10. ECG normal, or abnormal and not clinically significant.
11. FEV1 >80% of predicted.
12. Systolic blood pressure \geq 90 mmHg.

WEIGHT

Group 2 Only:

13. Body mass index (BMI) within the range 18 – 32 Kilogram (kg)/ meter (m)² (inclusive).

SEX

14. Female.

Group 2, Cohort A Only:

A female subject is eligible to participate if she is confirmed to be not pregnant at screening and on Day 1 (as confirmed by a negative serum or urine human chorionic gonadotrophin (hCG) test), not lactating, and the following condition applies:

- a. Is of reproductive potential and agrees to use the same **combined estrogen and progestogen oral contraceptive** from 3 months prior to the first dose of study medication and until the follow-up contact.

This method of contraception is only effective when used consistently, correctly and in accordance with the product label. The investigator is responsible for ensuring that subjects understand how to properly use their method of contraception.

Group 2, Cohort B Only:

A female subject is eligible to participate if she is confirmed to be not pregnant at screening and on Day 1 (as confirmed by a negative serum or urine hCG test), not lactating, and one of the following conditions applies:

- a. Is of reproductive potential and has been using the same **non-hormonal contraceptive method** (see List of Acceptable Nonhormonal Methods for Avoiding Pregnancy in Females of Reproductive Potential [see [Appendix 5](#)] from 3 months prior to the first dose of study medication and until the follow-up contact.
- b. Would be of reproductive potential, but has undergone bilateral tubal ligation or occlusion or bilateral salpingectomy at least 12 months prior to first dose of study medication.
- c. Is of reproductive potential with only same sex partners or who are and will continue to be abstinent from penile-vaginal intercourse on a long term and persistent basis, when this is their preferred and usual lifestyle. Periodic abstinence (e.g. calendar, ovulation, symptothermal, post-ovulation methods) and withdrawal are not acceptable methods of contraception.

These methods of contraception are only effective when used consistently, correctly and in accordance with the product label. The investigator is responsible for ensuring that subjects understand how to properly use their method(s) of contraception.

Of Note: Group 2, Cohort B will enrol women of reproductive potential if they agree to use a nonhormonal contraceptive method from at least one month prior to receiving study drug and until the follow-up assessment. Although condoms with spermicide are not considered a highly effective method of contraception, the risk of receiving study drug during pregnancy is minimal for the following reasons:

- Pregnancy testing must be negative at screening and on the first day of dosing.
- Dosing is completed no greater than 14 days from the start of dosing.
- Oxytocin has a well established rapid half-life.

If a patient happened to conceive during the time of dosing, study drug would be eliminated before implantation would occur.

INFORMED CONSENT**All Groups:**

15. Capable of giving signed informed consent as described in Section [10.2](#) which includes compliance with the requirements and restrictions listed in the consent form and in this protocol.

